Study Design	
Study design: Pilot randomized, single site clinical trial with blinded analysis
 
Participant recruitment and study site: We will recruit participants interested in using the ENG contraceptive implant but not currently at risk for pregnancy from University of Utah Hospital and Community clinics, and through targeted social media ads. All study procedures will occur at the University of Utah Hospital Outpatient OBGYN Clinic
 
Sample size: This is a pilot proposal to recruit a total of 40 participants across 2 study arms: (1) ENG implant only (n=20) and (2) UPA + same day ENG implant insertion (n=20). Our null hypotheses are:
 
 
1) ENG implant along with UPA administration in the presence of a dominant ovarian follicle will not change the expected 97% ovulation suppression within 5 days of UPA use.
 
2) ENG implant insertion alone in the presence of a dominant ovarian follicle will not sufficiently interrupt ovulation.
 
 
Inclusion criteria: Healthy people, age 18-35 years, fluent in English and/or Spanish, BMI < 30 kg/m^2, no known contraindication to either the ENG contraceptive implant or UPA using the CDC Medical Eligibility Criteria for Contraceptive Use 2016, not currently pregnant and not at risk of pregnancy (defined as not having penile-vaginal intercourse or using a non-hormonal method of contraception such as a barrier method, condoms, diaphragm, or cervical cap, a copper IUD, or permanent contraception), know the date of their last menstrual period, have a regular menstrual cycle (24-35 days), be willing to comply with the study requirements, and be willing to avoid pregnancy for study duration.
 
Exclusion criteria: Current pregnancy or breastfeeding, use of hormonal contraception or exogenous hormones (estrogen, progestogen, or HCG) in the last month (or past 6 months for depo medroxyprogesterone acetate) planned use during the study, vaginal bleeding of unknown etiology, allergy to UPA or ENG, regular or planned use of glucocorticoids during the study, or current or planned use of any medication that potentially interacts with UPA or ENG.
 
Participant adherence: Screening protocol will ensure willingness to comply with all study procedures. Participants will receive compensation for each component of the protocol.

Study Flowchart	<pre> graph TD     A[Phone Screening for Eligibility] --> B[Screening Visit 1- history, exam, TVUS]     B --> C[Screening Visit 2- Day 20-24 progesterone]     C --> D[Screening Visit 3-7 (+/-2)- Start TVUS 3X/week on day 7, then daily when follicle ≥ 13mm]     D --> E[Treatment Visit 1 (Follicle ≥ 14mm) – Randomization TVUS, serum LH, P4 and E2]     E --> F[Group 1- ENG Implant]     E --> G[Group 2- oral UPA + ENG Implant]     F --> H[Treatment Visit 2-8 (days 2,3,4,5,6,7,8)- TVUS, serum LH, P4 and E2]     G --> H     H --> I[Exit Visit (Treatment Day 14)- TVUS, serum LH, P4 and E2]   </pre>
Study Procedures	
Randomization scheme: block randomization with block size of 4
 
Blinding protocol: This study will not be blinded as a pilot. The feasibility of the study, including clinic space limitations and provider time, relies on the same healthcare provider for implant insertion and ultrasound in many patients. All statistical analyses will be blinded to the statistician.
 
Participant procedures:
 
Screening Visit (Screening Visit 1): Subjects will be screened for eligibility and interest in the study. Each subject will have the study explained and, if they desire to participate, she will sign the informed consent prior to any study procedures. The screening visit will include: review of medical, surgical and social history, medications, menstrual dating, sexual history and contraceptive use, physical exam, including breast and pelvic, and a transvaginal ultrasound to ensure ability to document ovarian follicular activity in the treatment cycle.
 
Progesterone Visit (Screening Visit 2): This brief visit will occur on days 20-24 of the menstrual cycle and may be combined with the screening visit (Visit 1) if the timeframe is met. This visit will include a review of any interim changes (if completed separate from the screening visit) in history, medications, pregnancy risk/contraception, and a serum progesterone level will be drawn. The participants will notify the study coordinator of the 1st day of their next menses.
 
Ovarian monitoring (Screening Visits 3-7 +/- 2 visits): Participants will undergo transvaginal ultrasound evaluation of their ovaries three times a week starting on cycle day #7 (+/- 2 days). If/ When we identify a lead follicle with a mean diameter of >13mm in at least 2 dimensions, we will switch to daily monitoring.
 
Treatment Day #1 (Treatment Visit #1): Once a lead follicle (<math>\geq 14mm</math>) is identified then participants will be randomized to one of two treatment groups:
 
 
1) ENG implant insertion
 
2) UPA 30mg PO tablet and same-day ENG implant insertion
 
 
Assigned treatment will be administered (UPA and/or ENG implant insertion). We will obtain serum progesterone, LH levels, and estradiol levels.
 
Treatment Days #2-8 (Treatment Visits #2-8): Participants will follow up daily for Days 2-8. Each day we will obtain transvaginal ultrasound measurement of ovarian follicle size, serum progesterone, LH levels, and estradiol levels. We will obtain daily


	
transvaginal ultrasounds until either follicle rupture is documented, the follicle is <12 mm on two consecutive visits, or Day 8 ultrasound occurs (7 days after implant insertion), whichever occurs first.
 
Treatment Day #14 (Exit Visit): Repeat ultrasound will occur on Day 14 following ENG implant insertion, and this will be the exit visit.
 
Data collection: Source documents for each participant and visit number will be completed by the study personnel at the time of the visit. Form development, data collection, and data management will occur in RedCAP, secure web platform for building and managing online databases and surveys. Source documents maintained in individual participant binders.
 
Assessing and reporting adverse events: The reporting period for AEs is the period immediately following the subject signing the informed consent through the 30 days following the final study visit. Each visit will include assessment of how the participant felt since the last visit, review of adverse event reports, implant insertion site reactions, lab results, and vital signs and physical exam findings. AEs will not be reported for screen failures unless a SAE is experienced during screening. For all AEs, the investigator will pursue and obtain information adequate to determine the outcome of the AE and to assess whether it met criteria for a SAE. Participants who have ongoing AEs or SAEs will be followed until resolution or stabilization or referred for additional care. AEs will be documented both on source documents and in the clinical database with SAEs reported per IRB guidelines. Participants will be provided instructions for contacting the study site to report any untoward medical occurrences. With permission from the participant, whenever possible records from all non-study medical providers related to medical occurrences will be obtained for review. AEs and SAEs will be reviewed by the Data Safety Monitoring Board as below (section 2.9).


Statistical Analysis Plan
	
The investigator and study team will be responsible for analyzing the study data. The official clinical database in RedCAP will not be analyzed until medical/scientific review has been completed, protocol violators have been identified (if appropriate), and data has been declared complete.
 
Variables/Time Points of Interest
 
The primary outcome is delay in rupture of the dominant follicle by 5 days (yes/no) between group 1 (ENG implant alone) and group 2 (UPA with same day ENG implant). If the date of follicle rupture was unclear by ultrasound alone, we will utilize serum hormone levels to adjudicate day of rupture. These measures include day of follicle collapse, day and value of highest LH, day and value of highest progesterone level. We will use an estradiol level of >100pg/ml to confirm the enlarged follicle is the dominant follicle on the treatment day.
 
Statistical Methods
 
The primary and secondary dichotomous outcome measures of ovulation by 5 days will be assessed by Wilcoxon sign rank test and demographic will be analyzed using descriptive statistics.
 
Power/Sample Size:
 
This is a pilot study to obtain point estimates for future study proposals. Current data on ovulatory function with mid-cycle implant insertion or the pharmacodynamics interactions between same day UPA and ENG are lacking.

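### In the text available, the planned between-arm analysis does not address the two stated null hypotheses, and no confidence intervals are planned

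*Combined protocol and SAP*

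**What the plan says.** Under Study Design, the sample size paragraph sets out a 40-person pilot with two arms of 20: etonogestrel (ENG) implant alone, and ulipristal (UPA) with a same-day implant. No arm receives UPA alone. Two null hypotheses follow.

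- Null 1: "ENG implant along with UPA administration in the presence of a dominant ovarian follicle will not change the expected 97% ovulation suppression". The window attached to that figure is the 5 days after UPA is taken.
- Null 2: "ENG implant insertion alone in the presence of a dominant ovarian follicle will not sufficiently interrupt ovulation".

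The Statistical Analysis Plan, under Variables/Time Points of Interest, gives the primary outcome as "delay in rupture of the dominant follicle by 5 days (yes/no) between group 1 (ENG implant alone) and group 2", the second being the UPA-plus-implant arm. Under Statistical Methods it says the dichotomous "outcome measures of ovulation by 5 days will be assessed by Wilcoxon sign rank test", and that demographics will be described. Under Power/Sample Size it says: "This is a pilot study to obtain point estimates for future study proposals".

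The text available gives no significance level, power, margin, decision rule, reference value for the test or confidence interval.

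**The concern.** Each null concerns a single arm, whereas the only outcome analysis compares the two arms. Null 1 sets the UPA-plus-implant arm against an external figure, and that figure appears nowhere in the analysis. Null 2 turns on the word *sufficiently*, which has neither a number nor a stated comparator, so it cannot be tested as worded.

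The outcome wording also shifts between suppression of ovulation, delay in rupture, and ovulation by 5 days. The documents therefore do not establish that the 97% and the trial's outcome measure the same thing.

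No decision rule hangs on the nulls, so what is at stake is what may be concluded. A between-arm result could be reported as an answer to null 1 when it is not one. Null 1 also puts *no change* in the null, so a small trial that fails to contradict it may be read as showing that the UPA effect is preserved. And the point estimates meant to support later proposals would carry no statement of their uncertainty.

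**Working it through.** **Inputs from the documents.** n = 20 per arm; reference rate 97% (null 1); a yes/no outcome. The plan gives no power or precision calculation, so there is no figure of its own to reproduce.

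**Assumptions.** 95% intervals, no dropout, Newcombe's method for the difference, illustrative counts, and illustrative true rates of 80%, 85% and 90%. Counts are participants with ovulation suppressed at 5 days.

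**Step 1: exact interval for one arm.** The Clopper-Pearson limits for x out of n are the 0.025 quantile of Beta(x, n-x+1) and the 0.975 quantile of Beta(x+1, n-x). At x = n the lower limit is 0.025^(1/n), so for 20/20 it is 0.025^(1/20) = 0.832.

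| Count | Exact 95% CI | Contains 97%? |
|---|---|---|
| 20/20 | 83.2-100% | yes |
| 19/20 | 75.1-99.9% | yes |
| 18/20 | 68.3-98.8% | yes |
| 17/20 | 62.1-96.8% | no |
| 14/20 | 45.7-88.1% | no |

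**Step 2: does the between-arm result answer null 1?** Newcombe's interval for d = p1 - p2 uses each arm's Wilson limits (l, u):

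- lower = d - sqrt[(p1-l1)^2 + (u2-p2)^2]
- upper = d + sqrt[(u1-p1)^2 + (p2-l2)^2]

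For 19/20 (Wilson 0.764-0.991) v 10/20 (Wilson 0.299-0.701), d = 0.45:

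- lower = 0.45 - sqrt(0.186^2 + 0.201^2) = 0.176
- upper = 0.45 + sqrt(0.041^2 + 0.201^2) = 0.655

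| UPA + implant v implant alone | Difference, points (95% CI) | UPA + implant exact CI | Contains 97%? |
|---|---|---|---|
| 14/20 v 14/20 | 0 (-26.8 to 26.8) | 45.7-88.1% | no |
| 19/20 v 10/20 | 45 (17.6 to 65.5) | 75.1-99.9% | yes |

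The first row shows no difference between arms while contradicting 97%. The second shows a large difference while remaining compatible with 97%. The between-arm result therefore does not determine the answer to null 1.

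**Step 3: does an interval containing 97% show preserved suppression?** From Step 1, the interval contains 97% only at 18/20 or more. With X ~ Binomial(20, p), P(X ≥ 18) = 1 - P(X ≤ 17):

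- true 90%: 1 - 0.323 = 0.677 (68%)
- true 85%: 1 - 0.595 = 0.405 (40%)
- true 80%: 1 - 0.794 = 0.206 (21%)

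So if suppression had really fallen to 90%, about two trials in three would still give an interval containing 97%.

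**Step 4: could null 1 be tested directly?** At p = 0.97, P(X ≤ 18) = 0.120 and P(X ≤ 17) = 0.021. A one-sided exact binomial test at 5% therefore rejects at 17/20 or fewer, with size 0.021. Its power is P(X ≤ 17): 32% at a true 90%, 60% at 85% and 79% at 80%. Because 0.97^20 = 0.544, even 20/20 could not show an improvement on 97%.

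**Step 5: null 2.** No calculation is possible without a threshold or a comparator.

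**The case against.** The strongest defence is that this is a 40-person pilot whose stated purpose is estimation. With no significance level or decision rule, the nulls read as motivation, and arm proportions are what such a study would naturally report. That stands, and it keeps the matter modest. It does not supply the missing intervals, a role for the 97%, or a meaning for *sufficiently*.

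Several stronger readings are tempting, and the documents do not support them.

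- *No matching analysis exists anywhere in the protocol.* The protocol refers to a section 2.9 that is not in the text available, so the point can be made only about that text.
- *Null 2 could never be rejected.* If *sufficiently* means relative to UPA plus implant, the between-arm comparison bears on it. The comparator is simply not stated.
- *The signed-rank test would be run on one arm against 0.97 and would mislead.* The plan gives no such reference value and defines its outcome between groups, so it does not propose that analysis. That a signed-rank test does not suit two independent binary arms is a separate defect.
- *The 97% rests on a different outcome.* Its source is not shown, and the two phrases in the analysis plan may simply be complements of each other. This is a question for the sponsor.
- *The nulls must be abandoned.* Making them testable is also acceptable.

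**Conclusion.** The concern holds for the text available and should be fixed. The planned comparison does not answer null 1, and null 2 is not testable as worded. With 20 per arm, no result can show that suppression stayed at 97%: the best possible count leaves a lower limit of 83.2%. The mismatch between nulls and analysis follows from the wording alone; the sizes rest on the 95% level, full follow-up and the illustrative counts and true rates. No error in the sample size of 40 is claimed, and the remedy agrees with the plan's own estimation purpose.

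**What to change.** 1. Use one outcome wording in the Study Design section and the Statistical Analysis Plan, for example: *no rupture of the dominant follicle by 5 days (yes/no)*. The sponsor should state which study day that is. Study Procedures counts Day 8 as 7 days after insertion, so 5 days after insertion is Day 6 (1 + 5), whereas Day 5 is only 4 days after.
2. Delete the signed-rank sentence under Statistical Methods. Replace it with: *We will report the difference between arms (UPA + ENG minus ENG alone) in the proportion without rupture by 5 days, with a 95% confidence interval for independent proportions (Newcombe), and each arm's proportion with its exact (Clopper-Pearson) 95% confidence interval.*
3. Choose one of two routes for the nulls.
   - Restate them as estimation aims. Show the 97% beside the UPA-plus-implant estimate descriptively, and only after the sponsor confirms that it rests on the same outcome definition and follicle-size entry criterion.
   - Keep null 1 with a one-sample exact binomial test, stating its rejection region and power (Step 4), and give *sufficiently* in null 2 a pre-specified number with its reason.
4. On either route, add: *Neither an interval containing 97% nor a between-arm interval containing 0 is evidence of no interference or of equality.*

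The cost is wording only: visits, measurements, allocation and sample size are unchanged. The downside is a weaker claim about preservation of the UPA effect and, on the estimation route, no p-value to cite.

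### One printed block size of 4 in an unblinded, single-site trial lets staff who know it and see every allocation deduce up to about a third of upcoming arms, while an ultrasound reading sets the day of entry

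*Combined protocol and SAP*

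**What the plan says.** All of this is in the combined protocol and SAP.

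- **Study Procedures, Randomization scheme:** "block randomization with block size of 4". One size is given. No variation in size and no strata are described.
- **Study Design:** a single-site pilot with 40 participants, 20 per arm.
- **Study Procedures, Blinding protocol:** "This study will not be blinded as a pilot". Feasibility "relies on the same healthcare provider for implant insertion and ultrasound in many patients". Only the statistician's work is blinded.
- **Study Procedures, Ovarian monitoring:** scans run three times a week from about cycle day 7. After a lead follicle above 13 mm is seen, "we will switch to daily monitoring".
- **Study Procedures, Treatment Day #1:** once a lead follicle of at least 14 mm "is identified then participants will be randomized to one of two treatment groups". After the sentence on giving the assigned treatment, the text adds "We will obtain serum progesterone, LH levels, and estradiol levels". It does not say whether the blood is drawn before or after treatment. The Study Flowchart puts "Randomization TVUS, serum LH, P4 and E2" in the same visit.
- **Statistical Analysis Plan:** estradiol above 100 pg/ml on the treatment day is used to confirm dominance. The primary outcome is a yes/no on delaying rupture by 5 days. The stated purpose is to supply point estimates for later proposals.

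**The concern.** When allocations are visible after the event, concealing the list does not stop people working out the tail of a short block of known size. With 1:1 blocks of 4, once two participants in a block have had the same arm, the rest of that block is known.

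This would matter little if entry followed a fixed calendar. Here it follows a measured follicle diameter. Someone who expects a particular arm could, on a borderline reading, bring entry forward or put it back by about a day. If that ran consistently by arm, follicle stage at treatment would differ between arms, and one day is a fifth of the 5-day window in the primary outcome. The pilot's point estimates would carry the difference into the next study. Shifts that did not run consistently by arm would not bias the comparison.

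**Working it through.** **Inputs.** Block size 4 (Randomization scheme); 40 participants, 20 per arm (Study Design); one site and no stated strata, hence one running sequence. Assumed, not stated: the observer knows the block size and has seen every earlier allocation in order.

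**The plan's own figure.** 40/4 = 10 complete blocks of 2 + 2, which gives 20 per arm. The scheme and the sample size agree. The plan states no figure for predictability.

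**Certain allocations, blocks of 4.** There are 6 equally likely orders. In AABB and BBAA the last two places are known in advance; in the other four only the last is. Expected number per block = (2×2 + 4×1)/6 = 4/3, and (4/3)/4 = 33.3%. Over 10 blocks this is 13.3 of 40, minimum 10, maximum 20, SD = √(10 × 1/3 × 2/3) = 1.5.

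**Best guess, blocks of 4.** Guess the arm with more places left. The chance of being right at places 1 to 4 is 1/2, 2/3, 2/3 and 1. The mean is (17/6)/4 = 17/24 = 70.8%, against 50% under simple randomisation.

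**Partial sight.** Assume instead that a provider sees each earlier allocation with probability f but still knows the position in the block. A certain deduction needs both same-arm allocations to have been seen, so the certain share is f²/3:

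| f | certain share |
|---|---|
| 1 | 33% |
| 0.9 | 27% |
| 0.75 | 19% |
| 0.5 | 8% |

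**Alternatives.** For one balanced list with n per arm, the certain share is 1/(n+1) and the expected number of correct guesses is n + (2^(2n)/C(2n,n) − 1)/2. Setting n = 2 returns 33.3% and 70.8%. Setting n = 20 gives 1/21 = 4.8% (1.9 of 40) and (20 + (7.976 − 1)/2)/40 = 58.7%. The 4/6/8 prediction figures are simulated, for an observer who knows the possible sizes but not their order. The constraint to end at 40 was imposed in three ways.

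| Scheme | Certain | Best guess right | SD of arm difference at 20 / 30 enrolled |
|---|---|---|---|
| Fixed 4 | 33.3% | 70.8% | 0 / 1.2 |
| 4/6/8 constrained to end at 40 | 5.3-6.0% | 68.2-68.7% | 1.0-1.1 / 1.1-1.2 |
| Single 20:20 list | 4.8% | 58.7% | 3.2 / 2.8 |

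For the single list, SD = 2√(m × 0.25 × (40 − m)/39) at m enrolled: 3.20 at m = 20 and 2.77 at m = 30. For fixed blocks of 4, 30 falls mid-block and SD = √(4 × 1/3) = 1.15. Unconstrained 4/6/8 would leave 27.5% of lists off 20:20 at 40, hence the constraint.

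**Price of imbalance under a single list.** A 2-SD imbalance is about 13:7 at 20 and 18:12 at 30. With equal variances the standard error of the difference rises by √((1/13 + 1/7)/(2/10)) = 1.048 and √((1/18 + 1/12)/(2/15)) = 1.021, that is by about 5% and 2%.

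**Power of a baseline check.** With 20 per arm, the 95% CI half-width for a mean difference is t(0.975, 38) × √(2/20) = 0.64 SD.

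**The case against.** The best case for the plan has four parts.

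1. **One third is a ceiling.** The sentence about the provider describes one person doing two tasks within a patient, in many patients but not all. It does not say that one person follows consecutive allocations, or who takes the qualifying scan. This stands, and is why the size is given as an upper figure with a range below it.
2. **The route to bias is narrow.** Consent precedes all study procedures, so selection into the study is not at issue. Deferring after a 14 mm reading would depart from the stated rule. What remains is shading a borderline diameter, in the same direction by arm. A follicle that passes 14 mm between the three-times-weekly scans leaves little to shade. This also stands.
3. **The estradiol criterion is a laboratory check.** This stands in part. It supports dominance, but it is not described as a condition for randomisation and does not fix the day of entry.
4. **Blocks of 4 suit a small pilot, and the remedy is modest.** They give exact balance at 40 and near balance on early stopping. Varied blocks lower the best guess by only two or three percentage points, and no list changes how unblinded staff read the scans after treatment. All true. The gain is in removing certain knowledge, not in removing guessing.

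A reader might go further and infer that allocation is unconcealed. The documents do not support that. The public text is incomplete, and who holds the list may be described in a part not shown. The point rests on the stated block size, which permits deduction even from a concealed list.

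**Conclusion.** The point holds as a minor weakness in a stated rule. Up to about a third of allocations on average could be known in advance, provided that staff know the block size, that there is one unstratified sequence, and that every earlier allocation is seen in order. That the size is constant is the plain reading of the one size given; that staff read the trigger scan is inferred from its being an ultrasound measurement.

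A reader might infer that the pilot's rupture estimates are biased. The documents do not support this: they show no shading, no motive and no direction, and no effect on the rupture rates can be computed. The finding is a limited opportunity to move the day of entry, in a setting where closing most of it costs little.

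**What to change.** Replace the single block size with undisclosed, randomly varied blocks (for example 4/6/8) constrained to end at 40. Keep block details out of the protocol text available to staff who scan or treat. Have REDCap, already in use for data collection, release the arm only after the qualifying follicle measurement has been saved. That last step protects the list but does not stop shading by someone who has already deduced the arm, so the less predictable list is the essential change.

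The cost is a new list, a sentence or two in the protocol, a list-holder outside scanning and treatment, and a small imbalance if enrolment stops early.

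A single concealed 20:20 list is a legitimate alternative. It lowers both certainty and guessing, but allows more imbalance on early stopping and gives up balance over calendar time, for example if the people scanning change. The sponsor should weigh the two.

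Optionally, report Treatment Day 1 follicle size, LH, progesterone and estradiol by arm. The hormones do not depend on the operator's reading. The comparison is valid only if samples are drawn before treatment, so the protocol should state the order. It would reveal only a large shift in follicle stage.

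### Using one provider for insertion and scanning does not by itself prevent masking the ultrasound reader, because both arms receive the same implant

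*Combined protocol and SAP*

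**What the plan says.** Under Study Procedures, Blinding protocol, the plan states: "This study will not be blinded as a pilot". The reason given is one of resources: "The feasibility of the study, including clinic space limitations and provider time", it says, "relies on the same healthcare provider for implant insertion and ultrasound in many patients". One masking measure follows: "All statistical analyses will be blinded to the statistician". I take this to mean that the statistician works without knowing the arms.

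Under Treatment Day #1 in the same section, group 1 has the ENG implant inserted and group 2 receives "UPA 30mg PO tablet and same-day ENG implant insertion". Study Design and the Study Flowchart show the same two arms, with 20 participants planned in each. The and/or phrase used just below the list of groups is loose, but the arm definitions and the flowchart make clear that everyone receives an implant.

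The Statistical Analysis Plan (Variables/Time Points of Interest) makes the primary outcome a yes/no call on whether rupture of the dominant follicle is delayed by 5 days. Ultrasound comes first, with hormones as a back-up: "If the date of follicle rupture was unclear by ultrasound alone, we will utilize serum hormone levels to adjudicate day of rupture".

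The documents do not say who gives the tablet, who decides that a scan is unclear, or that anyone reading scans or adjudicating rupture is masked.

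**The concern.** Whether and when a follicle has ruptured is a judgement made at the scan. If the person making it knows who took UPA, that knowledge can influence a borderline call, and the call is the primary outcome. The plan accepts this exposure for a reason that, taken alone, does not require it: inserting an implant that everybody receives does not reveal the arm.

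What is at stake is the main product of the pilot. The Power/Sample Size paragraph says that the study exists to supply point estimates for later proposals. An assessor effect would enter those estimates directly, and nothing later in the plan would remove it.

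**Working it through.** The plan states no figure that bears on this point. It gives no power, significance level or comparator rate, so there is nothing to reproduce. The check is mainly a comparison of sections, followed by simple arithmetic.

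1. **What differs between the arms** (Study Design; Study Flowchart; Treatment Day #1). Group 1: implant. Group 2: the same implant plus one oral UPA tablet. The tablet is the only difference.

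2. **What each task reveals.** Inserting the implant, or later seeing the insertion site, is the same in both arms and reveals nothing. Scanning reveals only the follicle. Opening the allocation or giving the tablet reveals the arm. One provider can therefore insert and scan while masked, provided that someone else does those last two tasks and the arm is not disclosed in some other way.

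3. **Where the existing safeguards sit.** The order is: ultrasound call; hormone adjudication if that call is judged unclear; database; statistician. Masking the statistician acts at the last step and cannot alter a call already recorded. Hormone adjudication acts only on scans labelled unclear, and a confident call made with knowledge of the arm bypasses it. A documented rupture also ends the daily scans (Treatment Days #2-8), so after such a call only the Day 14 scan is left to contradict it.

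4. **Size.** Let n = 20 per arm (Study Design) and let k be the number of calls in one arm changed in the same direction.
   - Change in that arm's rate = k/n. For k = 1, 1/20 = 5 percentage points; k = 2, 2/20 = 10; k = 3, 3/20 = 15.
   - One call changed in each arm, in opposite directions: 5 + 5 = 10 points on the difference. In the same direction: 5 − 5 = 0.
   - Illustration with assumed counts unruptured at 5 days: 19/20 in group 2 and 16/20 in group 1 differ by 95% − 80% = 15 points. One group 1 call changed to ruptured gives 15/20 and a difference of 20 points. One changed to unruptured gives 17/20 and a difference of 10 points.

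The 5 points per call depends only on n. The value of k cannot be derived from the documents, which do not say how often scans are borderline.

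**The case against.** **The choice is a disclosed, resource-based one.** The paragraph does not claim that masking is impossible. It cites pilot status, clinic space and provider time, and the role overlap applies to many patients, not all. If the inserting provider also gives the tablet, masking needs a second person at Treatment Visit 1, and provider time is the constraint named. This stands. A reader might infer that blinding was dropped needlessly; because the documents do not say who gives the tablet, they do not prove that.

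**The direction of bias is not shown.** A reader might infer that staff would favour UPA, since Study Design cites 97% suppression with UPA and says that the implant alone would not sufficiently interrupt ovulation. Both statements are set out as null hypotheses, and only the 97% is called expected. An assessor hoping that the implant alone works would lean the other way and narrow the difference. This stands too.

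**Significance examples prove little.** With assumed counts of 10/20 and 16/20 unruptured, Fisher's exact p is 0.096; changing one call in each arm gives 9/20 and 17/20, p = 0.019. It is tempting to conclude that two calls could decide the trial. But 97% of 20 is 19.4, so 16/20 with UPA does not match the plan's own expectation; at 10/20 and 19/20 the p-value is already 0.003. The pilot also sets no significance threshold.

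**Hormones are a real cross-check.** LH, progesterone and estradiol are scheduled daily over treatment Days 1 to 8, and unclear dates go to them. This limits the route by which bias could act but does not close it, because the person who may know the arm could also be the one who decides what is unclear.

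**Masking would be imperfect.** Without a placebo, participants know their arm. They attend up to seven daily follow-up scans and Day 14, and every visit includes questions about how they have felt and a review of adverse events. Some will disclose. That limits the gain without removing it.

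**Conclusion.** The point holds in limited form. The role overlap given as part of the reason for an open study does not by itself prevent masking the ultrasound reader, because both arms receive the same implant. As the plan stands, that reader may know the arm when making the primary-outcome call. Masking the statistician cannot correct this, and hormone adjudication does so only in part.

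The size is 5 percentage points on an arm's rate for each call influenced, assuming the planned 20 per arm are analysed. The documents show exposure to bias. They do not show that bias will occur, in which direction, or in how many participants.

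A reader might infer that this is a defect that must be corrected before the trial can run. The documents do not support that: unmasked conduct is openly stated in a 40-person pilot, and nothing here makes the data unanalysable. It is a worthwhile, cheap improvement.

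**What to change.** Amend the Blinding protocol paragraph so that:

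- existing staff other than the scanning provider open the allocation and give the tablet, or nothing, out of that provider's sight;
- allocation and dispensing records are kept out of the scan source documents;
- participants are asked not to tell the sonographer their arm;
- follicle size and rupture status are recorded before hormone results or allocation are seen;
- any unmasking of the scanning provider is logged.

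No placebo, extra reader, visit or procedure is needed, and the treatments are unchanged. The cost is a protocol wording change and a brief hand-off at Treatment Visit 1. This assumes that a second member of staff is free at that visit; the documents mention a study coordinator but do not describe such a duty. The downside is incomplete masking, since participants may disclose their arm, including during adverse-event review.

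Where a hand-off is not possible, the protocol should state the actual reason, and the report should list unmasked outcome assessment as a limitation.
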